Official Title: ASPIRE: A Study Promoting Critical Illness Recovery in the Elderly NCT02963558

IRB-Approved: 3/21/2023

ASPIRE: A Study Promoting Critical Illness Recovery in the Elderly

Principal Investigator:

D. [name]

Co-investigator(s):

[name]

Sponsor or funding source:

Wake Forest University Translational Science Center Wake Forest University Pepper Center Wake Forest University Critical Illness Injury and Recovery Research Center Wake Forest Center for Diabetes, Obesity, and Metabolism Departmental Start-Up Funds Ri, LLC (providing equipment only) NIA 1R03AG060076 - 01A1

Background, Rationale and Context

Advances in the care of critically ill patients have led to increased survivorship. However, survivors of critical illness are faced with a variety of short- and long-term complications, the most notable of which is intensive care unit acquired neuromuscular weakness (ICUAW).¹ Older patients have a higher incidence of acquiring a critical illness, and muscle wasting in this population appears more severe.^{2,3} Though we and others have shown that exercise administered during an intensive care unit (ICU) stay (early rehabilitation) can attenuate the severity of ICUAW,^{4,5} not all studies of rehabilitation have yielded positive outcomes.^{6,7}

Both pre-clinical animal studies from our lab and clinical studies suggest timing of rehabilitation may be key— EARLY (within 1-2 days) but not LATE (days 5 and beyond) initiation of ICU rehabilitation therapies in critically ill patients have generally led to improved functional outcomes.^{4,5,8-11} Unfortunately, significant barriers exist to the early implementation of ICU rehabilitation, most notably delirium and the use of sedating medications in the early phases of critical illness.¹²⁻¹⁴

[figure not shown]
In this proposal, we will test the hypothesis that EARLY application of a novel early rehabilitation therapy in critically ill patients will improve functional outcomes, and change the functional trajectory of this population. We will perform a pilot study of early mobilization with a cycle ergometer (MOTOmed, see Figure 1) and translate into humans the pre-clinical mechanisms that may mediate the effects of early mobility.

Figure 1: Use of a MOTOmed in a mechanically ventilated patient

Objectives

- To assess the feasibility of the application of a novel ICU early rehabilitation intervention.
- To obtain preliminary data to estimate the treatment effect size. This will allow power calculations for a larger, NIHfunded clinical trial.
- To understand if the application of a novel early ICU rehabilitation intervention attenuates the loss of muscle mass over time through inhibition of the E3 ubiquitin ligase muscle ring finger 1 protein.
- To determine the effects of exercise on energy utilization, mitochondrial function, and CPT-1 activity.
- 5) To determine the effects of the early ICU rehabilitation intervention on muscle mass.

6) To determine the effect of the early ICU rehabilitation intervention on quality of life in critically ill older adults.

Methods and Measures

Design:

Single-center randomized controlled pilot/phase II trial of a novel ICU early rehabilitation intervention.

Setting:

Wake Forest Baptist Medical Center Intensive Care Unit

Subject selection criteria:

Older adults with age \geq 55 years old who are critically ill with acute hypoxic respiratory failure requiring mechanical ventilation with an expected duration of \geq 3 days.

Inclusion Criteria

Age \geq 55 years old (Rationale: Older patients have a higher incidence of acquiring a critical illness, and muscle wasting in this population appears more severe. Therefore, this intervention may be most effective in this population.)

Admission to a Wake Forest Baptist Medical Center Intensive Care Unit

Acute Hypoxic respiratory failure on mechanical ventilation (MV) for <48 hours with a P:F ratio of <300 (or equivalent S:F ratio) with expected MV for at least 24 more hours

Previously Functional (over past 3 months, as reported by proxy): Physical Function: Able to walk 4 m (with or without assistive device)

Exclusion Criteria

Neuromuscular Disease Cardiopulmonary Arrest with return of spontaneous circulation <6 hrs Palliative Goals of Care; withholding life-sustaining therapy Raised Intracranial Pressure (>20 mm Hg) BMI>45; absolute weight >= 150 kg

Inability to cycle (including absent limbs, body length <1.5m, body habitus not fitting the cycle, inflammatory arthritis, significant joint problems including inability to bend arms/legs; pelvic and/or lower extremity fracture, lower extremity vascular bypass surgery)

Pregnancy

Use of continuous neuromuscular blockade Temporary Pacemaker or Swan Ganz catheter or femoral ECMO catheter/IABP Rhabdomyolysis with most recent CK >5000 Clinical Diagnosis of Dementia on Medication Moribund Possible Exclusion: If the patient is on spine precautions, a discussion with the spine team will be

necessary to determine eligibility for this study

Sample Size

We will randomize 21 subjects to the intervention group (novel ICU early rehabilitation) and 21 subjects to the control group. This sample size is based on the fact that this is a pilot proposal and that we want to optimize study procedures. We also have preliminary data which shows that this sample size might be large enough to detect a difference between groups based on SPPB at ICU discharge.

The primary analysis of the phase II part of the study is to compare SPPB at ICU discharge between the two groups using analysis of covariance (ANCOVA), adjusted for age, **sex**, and BMI. Under our assumptions of attrition (estimated at 15%) and mortality (SPPB=0 if patient has passed), with the current sample size (n=42), we will be able to detect an effect size of 0.98 or higher in the SPPB at ICU discharge with a power of 81% and a two-sided significance level of 0.05. This effect size is based on our pilot data and corresponds with the known minimal clinically important difference in SPPB of 0.5-1.3.^{15,16}

Interventions and Interactions

We will randomize patients to intervention or control groups. Patients will receive therapies according to their group assignment until hospital discharge or day 14, whichever comes first.

The intervention group will receive in-bed cycle ergometry within 48 hours of randomization if safety criteria (below) are met. In-bed cycle ergometry has been shown to be safe and feasible in the critically ill and is FDA-approved for use in this population.^{8,17-19} Subjects enrolled in the intervention arm will be screened at least 5 days per week to evaluate if they meet pre-defined safety criteria based on other studies of early mobilization and cycling in the ICU (see Table 1).^{4,5,8,17-20} Patients who meet the safety criteria will be positioned in the semi-recumbent position for cycling as per ICU guidelines. The cycler will provide 3 different possible modes of cycling—passive, active-assisted, and active. We will start with passive cycling and the patient may progress to active-assisted and active cycling. The goal duration of cycling will be 30 minutes. Subjects will receive in-bed cycling at least 5 times per week for the duration

[figure not shown]
of the ICU stay or until day 14, whichever comes first. During cycling and therapy sessions, study staff will also complete a case report form noting vital signs, level of mobilization, and other safety measures.

We have updated our safety criteria based on other completed and ongoing cycle trials in the critically ill (NCT03021902 and NCT03471247 and NCT02377830.) See table below.

	Daily Exemption Criteria	In-Session Stopping Criteria
Neurologic Criteria	 Uncontrolled Pain Severe Agitation with a RASS +3 or +4 	 Severe Agitation with a RASS +3 or +4
Respiratory Criteria	 Severe Agriation with a KASS +5 of +4 PEEP >15 FIO2 >80% 	 Unplanned Extubation Sustained O2 desaturation <85% Marked vent asynchrony
Circulatory Criteria	 An increase in vasopressor/inotrope by >5 mcg/min in past 2 hrs Levophed >50 mcg/min to maintain goal MAP Active myocardial ischemia Unstable or uncontrolled arrhythmia 	 Sustained symptomatic bradycardia (HR<40), tachycardia (HR>140), hypotension (MAP<60), or hypertension (MAP >130) Concern for myocardial ischemia New unstable or uncontrolled arrhythmia
Other Criteria	 Change in goals of care to comfort Team perceives therapy to be inappropriate (eg new hemorrhage, new wound) Patient Refusal 	 Catheter or tube dislodgement Team, subject, or surrogate request termination of session

In addition to cycling, the intervention arm will receive early physical therapy. This physical therapy (PT) will be performed according to a protocol of additional ICU and hospital-administered rehabilitation strategies previously developed in the Wake Forest MICU.⁴ Patients will receive 30 minutes of PT at least 5 times per week when they are conscious. If unconscious (as in Level 1 below), then they will only receive passive range of motion (PROM) for 10 repetitions per body part daily. Once conscious, subjects will progress through the different levels of PT with an emphasis on ambulation.

Therapy for the intervention arm patients will continue while on the floor. Outpatient therapy will be provided at the discretion of the patient's treating physicians.

The control group will receive usual care physical therapy as ordered by the treating team both in the ICU and on the floor through hospital discharge. These subjects will also receive therapy as outpatients only as ordered by their regular physicians.

Outcome Measure(s)

- 1) To assess the feasibility of the application of a novel ICU early rehabilitation intervention.
 - a. Primary Outcome for the pilot phase: Feasibility will be assessed by quantifying the ability to apply the MOTOmed device for at least a 15-minute session within 48 hours of randomization and meeting safety criteria.
- 2) To obtain preliminary data to estimate the treatment effect size. This will allow power calculations for a larger, NIH-funded clinical trial.
 - a. Short Physical Performance Battery (SPPB). We will measure SPPB at ICU and hospital discharge. Our primary outcome for the phase II study will be SPPB at ICU discharge.
 - b. Handgrip strength and dynamometry at ICU discharge and hospital discharge. ICU length of stay, Hospital length of stay will also be measured.
 - c. Healthcare utilization (ED visits, re-admissions) at 1, 3, and 6 months
 - d. Ventilator free days at 28 days.
 - e. Mortality at ICU discharge, hospital discharge, and 3 and 6 months
 - f. Short Form-36 (SF-36) at hospital discharge (in-person) and 3 and 6 months (by phone)
- 3) To understand if the application of a novel early ICU rehabilitation intervention attenuates the loss of muscle mass over time through inhibition of the E3 ubiquitin ligase muscle ring finger 1 protein.
 - a. Serial Skeletal Muscle Ultrasounds at days 0, 3, 5, ICU discharge, hospital discharge Muscle thickness, size and echogenicity in the vastus and the rectus femoris muscles
 - b. Serial Plasma at days 0, 1, 3, and 5 and ICU and hospital discharge
 - i. Plasma acylcarnitine profile
 - ii. Will be banked for future studies
 - c. Blood on 1st day of exercise (for 5 intervention patients only) will be evaluated for leukocyte kinetics in response to exercise (exploratory analysis) based on animal data. This is completed.

- 4) Pilot study: To determine the effects of exercise on energy utilization, mitochondrial function, and CPT-1 activity. Phase II: To determine the effects of exercise on energy utilization.
 - a. Continuous non-invasive CO2 monitoring, day 0 through day 5
 - b. Accelerometer activity monitor, day 0 through 2 weeks post-discharge.
 - c. Nutritional Assessments, blood sugar levels, day 0 through ICU discharge

TABLE 5: TESTING BATTERY	Day 0	Day 1	Day 3	Day 5	ICU D/C	Hosp D/C	Phone: 3 months	Phone: 6 months
Aim 1: Physical Function:								
Feasibility	х	х	х	Х	Х	Х	х	х
MAT-sf	Х				Х	Х		
SPPB					Х*	Х		
Handgrip/ quad strength					Х	Х		
MoCA / MoCA Blind					Х	Х	х	х
Aim 2 Muscle Mass:								
Ultrasound	Х		Х	Х	Х	Х		
Aim 3: Quality of Life:								
SF-36						Х	Х	х
Exploratory Outcomes:								
ICU LOS					Х			
Hospital LOS						Х		
Vent-Free Days (28)					Х	Х		
Healthcare Utilization							Х	х
Mortality					Х	Х	Х	х
Blood	Х	Х	Х	Х	Х	Х		
Energy	Х	Х	Х	Х	Х	Х		

Updated Testing Battery:

NB—Inpatient assessments may be completed up to 1 day before or after the specified time point, and may be carried over to another assessment. Outpatient assessments may be completed up to 2 weeks before or after the specified time point. Muscle biopsies may be performed up to 1 day before or 2 days after the specified time point.

Data Collection for demographics and baseline information: Demographic Information will be obtained on all patients. Additionally, the Acute Physiology and Chronic Health Evaluation (APACHE), Charlson index, and the comorbidity indices will be calculated. Other variables which will be collected will include medications and information about ICU and hospital stays.

Muscle ultrasounds will be completed per protocol with standard views required to examine the size and echogenicity of patient muscles. Gel will be applied to the skin, the ultrasound probe will be placed on the gel, and then with minimal pressure, the required images will be obtained. A Sonosite ultrasound machine will be used. Bony landmarks will confirm that the probe is placed perpendicular to the muscle. Images will be saved on a laptop computer and then analyzed with Image J software. The Short Physical Performance Battery (SPPB) is based on timed measures of standing balance, walking speed, and ability to rise from a chair. Each measure is assigned a score ranging from 0 to 4, with a total possible summary score of 12. The SPPB was developed for functional evaluation of the geriatric population. Given the target population of this study, this is an ideal instrument to measure physical function in this cohort.

Handgrip will be assessed with a Jamar hand-held dynamometer. Three trials with brief pauses will be performed for each hand. A recording of hand dominancy will also be made.

Skeletal muscle strength will be measured in the lower extremities. An electronic strength dynamometer (MicroFET 2MT Dynamometer, Hoggan Health Industries, Salt Lake City, UT) will be used to collect strength measures of the ankle and knee, bilaterally. Three trials with brief pauses will be performed for each muscle group. The best performance of three trials will be selected for each side.

Non-invasive continuous volumetric CO2 (vCO2) will be performed using either a NM3 device (*Phillips-Respironics*) or ventilator capable of vCO2 measurements. Daily energy expenditure (divided into 12 hour segments) will be calculated using the formula validated by Stapel et al. vCO2 measurements will not be used for clinical decision making. The use of NM3 device poses minimal harm to enrolled patients.

The activity monitors will be given to the patients when enrolled in the study to wear throughout their hospitalization. Patients will be asked to wear the accelerometer and return it in with a pre-paid envelope.

Health related quality of life will be assessed using the Short Form-36. The SF-36 is a self-reported generic measure of health related quality of life. It consists of 36 items which can be used to provide summary measures of physical and mental health and eight distinct dimensions of health.

The Montreal Cognitive Assessment (MoCA) and the MoCA- BLIND will be used to measure cognitive status. The MoCA and the MoCA-BLIND are validated tools of 22-30 questions which assesses: short-term memory recall, visuospatial abilities, executive function, attention, concentration, and working memory, language, conceptual thinking, calculations, and orientation to time and place. They are highly sensitive and specific to detect mild cognitive impairment.

The Mobility Assessment Tool short form (MAT-sf) is a video animated tool for assessing self-perception of mobility. Items consist of a video and a corresponding measurement item. The video depicts a wooden mannequin performing a wide range of physical activities and the measurement item consists of a question about the participant's ability to perform the task, measured on a discrete scale.

Healthcare utilization and mortality will be determined through a variety of mechanisms including a review of the electronic medical record, phone calls to patients/ families/ contacts provided at the start of the study, and a query of the NC State Death Index.

Analytical Plan

Phase I pilot study:

Given that this is a pilot study, all analyses other than the feasibility assessment and basic descriptive statistics will be performed solely to inform a larger trial. Power calculations will not be utilized for this study given it is a pilot study.

Version 4 9/6/2019 We have a growing ICU population over the past 5 years. In 2013 alone, we had >1300 older adults admitted to just the MICU. Thus, we should have a large population of patients on which to draw from for enrolment in the study.

Patient demographics will be evaluated with descriptive statistics. The objectives will be evaluated as described below.

- The feasibility of compliance to the application of the novel ICU early rehabilitation intervention will be assessed by the number of patients in the intervention arm out of the total intervention patients (10) who are able to undergo a 15 minute cycling session within the first 48 hours of randomization and meeting safety criteria.
- 2) SPPB, handgrip strength/dynamometry, calorimetry, ICU and hospital lengths of stay, healthcare utilization (SPPB), ventilator-free days, mortality, and SF-36 and MoCA scores will all be analyzed with descriptive statistics. Tests for trend will be evaluated and adjusted analyses will also be performed. Analysis of co-variance will be used, adjusted for age, gender, and BMI and other adjusted analyses will be performed as necessary. We will also explore the longitudinal effect of the intervention with linear mixed effect models.
- And 4) Muscle ultrasound measures, skeletal muscle biopsy measures, and plasma analyses will also be analyzed with descriptive statistics, tests for trend including with linear mixed effect models, and adjusted analyses.

In sum, results will be analyzed initially using descriptive statistics. Comparison between groups will be done using chi square tests for proportions, and t-tests or ANOVA procedures for continuous variables. Regression analysis will be performed to identify independent outcome predictors. Other inferential statistical analysis will be conducted as appropriate.

Phase II: The primary analysis is to compare SPPB at ICU discharge between the two groups using analysis of covariance (ANCOVA), adjusted for age, gender, and BMI. Under our assumptions of attrition (estimated at 15%) and mortality (SPPB=0 if patient has passed), with the current sample size (n=42), we will be able to detect an effect size of 0.98 or higher in the SPPB at ICU discharge with a power of 81% and a two-sided significance level of 0.05. This effect size is based on our pilot data and corresponds with the known minimal clinically important difference in SPPB of 0.5-1.3.^{15,16} We will perform similar analyses for SPPB at hospital discharge and explore the longitudinal effect of the intervention, using linear mixed effect models to compare the trajectories of SPPB over time. We will analyze secondary outcomes including hand grip, quadriceps dynamometry, RF CSA and echogenicity, quadriceps depth, TA depth and echogenicity, and QOL in a similar fashion. For this study, the services of the Pepper Center Biostatistics and Research Information Systems Core will be used.

Human Subjects Protection

Please see attached document.

Subject Recruitment Methods

Our ICU research team will screen patients admitted to the ICU for inclusion/ exclusion criteria for entry into the study. We will only access necessary information (using a minimal amount of PHI) for screening through the electronic medical record. PHI necessary will include name, geographic information, dates, telephone number, medical record, and access to this information will be sought under a limited HIPAA waiver. All information will remain confidential in a password protected file on a password protected

computer. If deemed eligible, subjects (or their surrogates if unable to consent for themselves) will be approached for consent. If the patient/ surrogate does not consent for the study, the study team will maintain a record of those not enrolled which will be kept in a password protected file on a password protected computer. This record will be destroyed 3 years after study completion and publication.

We will not differentially approach women or minorities for inclusion in this study. However, please note that given the small sample size of this project, we will likely have imbalances.

Informed Consent

Signed informed consent will be obtained from each subject or from a surrogate decision-maker. If a surrogate decision-maker is used for initial consent, then when the patient is mentally able to consent for him/herself, he/she will be re-approached by the study coordinator or investigators for consent. All consents will take place in the ICU.

Confidentiality and Privacy

Confidentiality will be protected by collecting only information needed to assess study outcomes, minimizing to the fullest extent possible the collection of any information that could directly identify subjects, and maintaining all study information in a secure manner. To help ensure subject privacy and confidentiality, only a unique study identifier will appear on the data collection form. Any collected patient identifying information corresponding to the unique study identifier will be maintained on a linkage file, stored separately from the data. The linkage file will be kept secure, with access limited to designated study personnel. We will input data into the RedCAP web based data entry system as it is highly secure and is regularly backed up. Following data collection subject identifying information will be destroyed three years after publication of the study, consistent with data validation and study design, producing an anonymous analytical data set. Data access will be limited to study staff. Data and records will be kept locked and secured, with any computer data password protected. No reference to any individual participant will appear in reports, presentations, or publications that may arise from the study.

Data and Safety Monitoring

The principal investigator will be responsible for the overall monitoring of the data and safety of study participants. The principal investigator will be assisted by other members of the study staff.

Additionally, a Data and Safety Monitoring Board will be convened by the PI. This DSMB will monitor all serious/unexpected adverse events as well.

Reporting of Unanticipated Problems, Adverse Events or Deviations

Any unanticipated problems, serious and unexpected adverse events, deviations or protocol changes will be promptly reported by the principal investigator or designated member of the research team to the IRB and sponsor or appropriate government agency if appropriate.

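### Does the missing unit and SD behind the 0.98 effect size undermine the 81% power statement for SPPB at ICU discharge?

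*Combined protocol and SAP*

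**What the plan says.** The Sample Size section fixes the numbers: "We will randomize 21 subjects to the intervention group (novel ICU early rehabilitation) and 21 subjects to the control group". It gives two reasons. The first is that this is a pilot in which procedures are to be refined. The second is that preliminary data suggest the size might be enough to show a difference in SPPB at ICU discharge. The primary analysis is an ANCOVA adjusted for age, sex and BMI.

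The power statement allows for 15% attrition, scores deaths as 0 and uses a two-sided 0.05 level. It says that "we will be able to detect an effect size of 0.98 or higher in the SPPB at ICU discharge with a power of 81" per cent, and continues: "This effect size is based on our pilot data and corresponds with the known minimal clinically important difference in SPPB of 0.5-1.3". The Phase II paragraph of the Analytical Plan repeats this.

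The measures text after the testing battery table describes the SPPB scale: "Each measure is assigned a score ranging from 0 to 4, with a total possible summary score of 12". No SPPB mean, SD, mortality rate or covariate R-squared appears anywhere, and 0.98 has no unit.

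**The concern.** An effect size quoted without a unit usually means a difference divided by an SD. An MCID for a 0-12 score is naturally read in points. Two numbers on different scales can be compared only through an SD, and none is given. The sentence that links them therefore looks unsupported, and it could mislead a reader into thinking that the trial has 81% power for any clinically important difference.

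If the SD were well above 1 point, the smallest difference detectable with 81% power would exceed the top of the MCID range, and the trial would be weaker than the text suggests on its phase II primary outcome. Item 2 of Outcome Measure(s) adds apparent weight, because it says of the data on effect size: "This will allow power calculations for a larger, NIH-funded clinical trial".

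**Working it through.** **Inputs from the documents.** 21 per arm; 15% attrition; two-sided 0.05; effect 0.98; stated power 81% (Sample Size, repeated under Phase II in the Analytical Plan). Three covariates. MCID 0.5-1.3, unit not stated. SD not stated.

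**Step 1: reproduce the 81%.** Evaluable patients: 42 × 0.85 = 35.7, or about 18 per arm. For a standardised difference d with n per arm, the noncentrality is d / √(2/n) = 0.98 / √(2/18) = 0.98 / 0.3333 = 2.94, on 36 − 2 = 34 degrees of freedom. The noncentral t distribution gives:

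| Evaluable per arm | Power at d = 0.98 | With 3 covariate df |
|---|---|---|
| 18 and 18 | 81.5% | 81.3% |
| 17.85 and 17.85 | 81.1% | 80.9% |
| 18 and 17 | 80.3% | 80.1% |
| 21 and 21 (no attrition) | 87.3% | 87.1% |

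The plan's figure is recovered from its own inputs if 0.98 is in SD units. It is recovered equally if 0.98 is in points and the SD is about 1.0 (1.006 points gives exactly 81% at 18 per arm).

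**Step 2: when does 0.98 fall inside the MCID range?**

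- *0.98 in points:* it lies between 0.5 and 1.3, and the text is consistent, given an SD of about 1.0.
- *0.98 standardised, MCID in points:* the detectable difference is 0.98 × SD. The limits are 0.5 / 0.98 = 0.51 and 1.3 / 0.98 = 1.33, so the match holds for an SD of about 0.51 to 1.33 points. For an ANCOVA this is the residual SD. If the covariates explained 20% of the variance (an assumption), the upper limit on the raw SD would be 1.33 / √0.8, about 1.48.

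**Step 3: dependence on the SD.** Every SD below is an assumption, with 18 per arm.

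| SD (points) | 0.98 × SD | Power at 0.5 points | Power at 1.3 points |
|---|---|---|---|
| 0.51 | 0.50 | 81% | >99% |
| 1.0 | 0.98 | 31% | 97% |
| 1.33 | 1.30 | about 20% | 81% |
| 1.5 | 1.47 | 16% | 71% |
| 2 | 1.96 | 11% | 47% |
| 3 | 2.94 | 8% | 24% |

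**Step 4: can the documents settle the SD?** They cannot. Two invented distributions show this.

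- *Half the patients at 0, the rest with mean 2 and SD 1:* the overall mean is 1 and the variance is 0.5 × (1 + 4) − 1 = 1.5. The SD is 1.22 and the detectable difference is 0.98 × 1.22 = 1.20 points, inside the range.
- *One fifth at 0, the rest with mean 3 and SD 2:* the overall mean is 2.4 and the variance is 0.8 × (4 + 9) − 5.76 = 4.64. The SD is 2.15 and the detectable difference is 0.98 × 2.15 = 2.11 points, outside it.

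Nothing in the documents favours one over the other.

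**The case for a change.** The strongest case for a change is that this power statement supports the named phase II primary comparison and makes an explicit clinical claim. If 0.98 is standardised, setting it beside a range in points without an SD is a step that the reader cannot follow. Pilot status does not excuse that, because the same section chose to make the claim. The effect is said to come from pilot data, so the SD should be to hand, and stating it would take a few words in two paragraphs.

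One part of this stands: the unit and the SD are absent, and the MCID sentence cannot be verified from the text. The rest is weaker.

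- The plan claims 81% power for effects of 0.98 or more. It does not claim that power throughout 0.5-1.3, so low power at 0.5 points contradicts nothing it says. Powering at one value within an MCID range is ordinary practice.
- The larger trial mentioned under Outcome Measure(s) would be planned from the means and SD that this trial observes. A missing planning SD does not hinder that.
- Power is not the only basis for 42 patients. The pilot purpose comes first, and the claim from preliminary data is hedged.
- That the MCID is in points is a sensible reading, but the documents do not say so. The low powers at SDs of 2 or 3 rest on assumed values and do not demonstrate a shortfall.

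**Conclusion.** The concern does not call for a change. No stated number is wrong: 81% follows from 42 patients, 15% attrition and an effect of 0.98, either as a standardised difference or as 0.98 points with an SD of about 1.0. The sentence linking the effect to the MCID is uncheckable, which is not the same as false. It is consistent if 0.98 is in points. If 0.98 is standardised and the MCID is in points, it holds for an SD of about 0.51 to 1.33 points. These results assume about 18 evaluable patients per arm and a t-based comparison with no variance explained by the covariates.

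The gap is one of reporting. Writing down a unit and an SD, or removing the MCID sentence, would leave the 42 patients, the endpoint, the scoring of deaths and the ANCOVA exactly as they are. Once the data are in, the estimated difference in points and its confidence interval will show what the trial could distinguish, whatever SD was used in planning. A reader should meanwhile take the 81% as power for a standardised effect of about one SD, and should not read it as assurance of power at every difference within 0.5-1.3.

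### Does scoring death as SPPB 0 leave the primary comparison undefined, and does length of stay need its own rule for deaths?

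*Combined protocol and SAP*

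**What the plan says.** The primary Phase II analysis is an ANCOVA of SPPB at ICU discharge, adjusted for age, sex and BMI (Sample Size; Analytical Plan, Phase II). In both places the next statement is the power calculation, which opens "Under our assumptions of attrition (estimated at 15%) and mortality (SPPB=0 if patient has passed". It reports 81% power for an effect size of 0.98 with 42 patients and says that this effect "corresponds with the known minimal clinically important difference in SPPB of 0.5-1.3". The Phase II paragraph continues: "We will perform similar analyses for SPPB at hospital discharge", and adds mixed models of SPPB over time. Neither comes with a separate statement about deaths.

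On the instrument, Methods and Measures says: "Each measure is assigned a score ranging from 0 to 4, with a total possible summary score of 12". A living patient can therefore score 0.

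The Background states the hypothesis in terms of function: "we will test the hypothesis that EARLY application of a novel early rehabilitation therapy in critically ill patients will improve functional outcomes". One objective is "To obtain preliminary data to estimate the treatment effect size", for use in planning a larger trial. The Outcome Measures section lists "Mortality at ICU discharge, hospital discharge, and 3 and 6 months" as an outcome in its own right. On stay it says only "ICU length of stay, Hospital length of stay will also be measured", and Table 5 places both lengths of stay under exploratory outcomes. Their analysis methods appear only in the Phase I text.

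**The concern.** There are two separate points.

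The first is SPPB. The zero for death is worded as an assumption behind the power figure, not as an analysis rule. Taken literally, an analyst could score deaths 0 or leave them out, and the two choices estimate different things. If deaths score 0, a death equals the worst living result and the ANCOVA difference combines survival with function. The plan nevertheless speaks of function, sets the effect against a functional minimal important difference, and intends the estimate to inform a larger trial. A reader could mistake a composite for a gain in physical function, or a survival difference for a functional one.

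The second, lesser point is length of stay. If patients who die keep their observed stay, early deaths shorten the mean, and an arm with worse survival can look better.

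**Working it through.** **1. The stated power, and what it implies about deaths.** Inputs from the protocol: 21 per arm, 15% attrition, effect 0.98, two-sided 0.05, three covariates. The figure reproduces when 0.98 is read in standard deviation units.

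- Patients analysed: 42 × 0.85 = 35.7, taken as 18 per arm.
- Noncentrality: 0.98 / √(1/18 + 1/18) = 0.98 × 3 = 2.94.
- Noncentral t power: 81.5% unadjusted, 81.3% with three degrees of freedom spent on covariates. The stated figure is 81%.
- With no attrition (21 per arm): 87.3%.
- With deaths also removed, n per arm = 42 × 0.85 × (1 − q) / 2 for an assumed mortality q:

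| q | n per arm | power |
|---|---|---|
| 10% | 16 | 77% |
| 20% | 14 | 70% |
| 30% | 12 | 63% |

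The calculation fits one reading: losses are removed and deaths are kept with a score.

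**2. How much the composite differs from the survivor effect.** With death scored 0, the group difference is (1 − q1) × m1 − (1 − q0) × m0, where q is mortality and m the survivor mean. The documents give no mortality rate, so these are assumed. With equal mortality q this becomes (1 − q) × survivor gain. For the quoted 0.5 to 1.3 points:

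| q | appears as |
|---|---|
| 10% | 0.45 to 1.17 |
| 20% | 0.40 to 1.04 |
| 30% | 0.35 to 0.91 |
| 40% | 0.30 to 0.78 |

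With equal function in survivors but mortality of 15% against 25%, the difference is 0.10 × the survivor mean, or 0.2 to 0.6 points for means of 2 to 6. So the composite is diluted in one case and carries survival in the other. Unadjusted, the survivor mean is recoverable as composite mean / (1 − proportion dead).

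**3. Scoring deaths 0 against leaving them out.** Simulation: 18 per arm, three covariates unrelated to outcome, equal mortality, no treatment effect. The entries are the share of trials in which the two estimates differ by 0.5 points or more.

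| Assumed survivor scores | 10% mortality | 20% | 30% |
|---|---|---|---|
| 40% zeros, others uniform 1-10 | 20% | 37% | 49% |
| 40% zeros, others uniform 1-6 | 6% | 19% | 27% |
| 70% zeros, others uniform 1-6 | 1% | 6% | 15% |

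In the first row the standard error of the estimate is 1.14 to 1.20 points, so a 0.5-point shift is 0.42 to 0.44 of a standard error. The two rules disagree on p < 0.05 in 3% to 5% of those trials. At 20% mortality, with survivor zeros at 60% against 20% (a gain of 0.40 × 5.5 = 2.2 points), the mean estimates are 1.77 with deaths at 0 and 2.21 with deaths left out, and disagreement is 13%. With zeros at 50% against 30% (0.20 × 5.5 = 1.1 points) it is about 7.5%.

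**4. A ranked analysis with death below a living 0.** Simulated rejection rates under the uniform 1-10 model:

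| Scenario | ANCOVA | Ranked |
|---|---|---|
| Equal 20% mortality, zeros 60% v 20% | 33.5% | 26.4% |
| Equal 20% mortality, zeros 80% v 10% | 82.0% | 64.8% |
| Mortality 30% v 10%, averted deaths all at 0 | 5.1% | 9.4% |
| Same, half at 0 | 7.3% | 16.1% |
| Same, none at 0 | 15.3% | 25.5% |

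Ranking loses about 7 and 17 points when mortality is equal and gains 4 to 10 when it differs.

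**5. Length of stay.** Assume mortality of 30% against 10% and a survivor stay of 10 days. The mean difference for the better-survival arm is (0.30 − 0.10) × (10 − day of death): +1.0 day for deaths at day 5, 0 at day 10, −1.0 at day 15. The direction depends on an unknown. At 21 per arm, time to discharge alive reaches significance in 30% to 32% of simulated trials in this case, and a rank comparison with death worst in 19% to 21%. With equal 20% mortality and survivors leaving at 8 rather than 10 days, raw means point the right way in 76% to 80% of trials and time to discharge alive in 67% to 68%.

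**The case for a change.** The strongest case for a change is that the rule ought to be written as a rule. It is worded as an assumption, the mixed models are given no value for deaths, and nothing tells the reader that the primary difference includes survival. The patients are ventilated adults aged 55 or over, so deaths before ICU discharge are foreseeable, and fixing the scoring in advance prevents a choice made after the data are seen. The dilution in step 2 is algebra and does not depend on a simulated score distribution.

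Much of this stands as a remark on drafting. It does not show that the plan's analysis goes wrong:

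- Leaving deaths out is proposed nowhere and conflicts with the power statement, so the contrasts in step 3 measure the distance to an analysis the plan does not contain. They also shrink sharply under other plausible score distributions.
- The death score is not limited to ICU discharge, so the matching analysis at hospital discharge inherits it naturally. Only the mixed models are truly silent, and they are exploratory.
- For planning a larger trial, the composite is the right input if that trial scores death the same way. If it does not, the separately reported mortality allows the survivor mean to be recovered. Living zeros can be counted from the SPPB and mortality data already collected.
- Comparing the effect with the minimal important difference raises another question, because 0.98 reproduces in standard deviation units while the quoted range is for SPPB itself. That is separate from how deaths are scored.

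**Conclusion.** No change to the plan is needed. Scoring death 0 is a recognised choice. It keeps every randomised patient with a known outcome in the comparison, and its place beside the primary ANCOVA, together with the reproduced 81%, shows that it is the rule intended. An analyst following the text would score deaths 0 at both discharges and report mortality alongside, as the outcome list already requires. Calling the difference a composite and tabulating deaths, living zeros and survivor scores is good reporting, available from collected data, and leaves the method as it is.

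The real departures from the plan are trade-offs. Ranking death below a living 0 costs about 7 to 17 power points if mortality is equal and gains 4 to 10 if it is 30% against 10%. For length of stay, an exploratory outcome with mortality reported at the same time points, the alternative has low power and loses accuracy of direction when mortality is equal.

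The power result rests on reading 0.98 as standard deviation units. All mortality rates, score distributions and stay lengths are assumptions. The dilution by (1 − q) under equal mortality does not depend on the assumed score distribution.
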